		Serum samples will be used only for scientific research. Each sample will be labeled with a code so that the laboratory personnel testing the samples will not know the subject's identity. Samples that remain after performing assays outlined in the protocol may be stored by Pfizer. Unless a time limitation is required by local regulations or ethical requirements, the samples will be stored for up to 15 years after the end of the study and then destroyed. If allowed by the informed consent, stored samples may be used for additional testing to better understand the immune responses to the vaccines under study in this protocol, to inform the development of other products, and/or for vaccine related assay work supporting vaccine programs. No testing of the subject's genetic material will be performed. All serologic testing will be conducted by the National Institutes for Food and Drug Control (NIFDC). After completion of the study, all remaining serum samples will be under the custody of
		 The subject's parent/legal guardian may request that his or her child's samples, if still identifiable, be destroyed at any time; however, any data already collected from those samples will still be used for this research. The biological samples may be shared with other researchers as long as confidentiality is maintained and no testing of the subject's genetic material is performed. Rationale: Added specificity and clarity. Section 7.5: Added the information regarding NIFDC. Rationale: Added specificity and clarity.

Document	Version Date	Summary of Changes and Rationale
		- Section 9.2.2: The newly added text is italicized and underlined , the deleted text is highlighted with strikethrough:
		The proportion of subjects achieving an antibody IgG concentration $\ge 0.35 \ \mu$ g/mL, as well as the proportion of subjects with pneumococcal OPA titer $\ge -1:8 \ above \ a$ defined level will be computed for each tested blood sample obtained from subjects in all cohorts
		Rationale: Added specificity and clarity.
		- Appendix 1: Added NIFDC in the abbreviation table.
Amendment 2	endment 2 07 February 2019	 Protocol Summary, Section 1.2, Section 3.4, Section 7.5.1, Section 7.5.2, Section 9.4: Added the enrollment of additional 280 subjects from county CDCs. Rationale: To provide additional data in the event that only subjects recruited at municipal and county level CDCs should be included in vaccine clinical studies.
		- Section 3.4: Change "Randomized subjects withdrawn from the study will not be replaced, regardless of the reason for withdrawal" to "Randomized subjects who withdraw from the study may be replaced to maintain adequate numbers to achieve study objectives". Rationale: May need to recruit additional subjects due to higher than expected subject withdrawal in order to achieve study objective.
		 Section 7.5.2: Delete "13vPnC" from "the blood samples taken before vaccination and 1 month after the last 13vPnC vaccination in each of the 3 cohorts" in Cohorts 2, 3, 4. Rationale: Added

Document	Version Date	Summary of Changes and Rationale
		specificity and clarity.
		- Section 6.1.1, Section 6.2.1, Section 6.3.1, and Section 6.4.1: Change "including date of birth, sex and race" into "including full date of birth, sex and race. The date of birth will be collected to critically evaluate the immune response and safety profile by age". Rationale: Added specificity and clarity.
		- References: Updated to reflect changes.
		- Appendix 1: Added CDC in the abbreviation table.

This amendment incorporates all revisions to date, including amendments made at the request of country health authorities and institutional review boards (IRBs)/ethics committees (ECs).

TABLE OF CONTENTS

LIST OF TABLES	10
APPENDICES	11
PROTOCOL SUMMARY	12
STUDY DESIGN.	13
Description	13
STATISTICAL ANALYSIS	14
Immunogenicity Analysis Populations	14
Safety Analysis	14
Analysis Timing:	14
SCHEDULE OF ACTIVITIES	15
1. INTRODUCTION	19

Appendix 1. Abbreviations

PROTOCOL SUMMARY

This study is designed to support licensure of 13-valent Pneumococcal Conjugate Vaccine (13vPnC) through 5 years of age.

This study includes 4 separate cohorts broken down by age. Cohort 1 will include infants 6 weeks to 2 months of age that will be vaccinated with 13vPnC according to the currently licensed infant schedule (2, 4, 6 and 12 to 15 months). Cohorts 2, 3 and 4 range in age from 7 months to 5 years of age (Cohort 2 - 7 months to <12 months of age; Cohort 3 - \geq 1 year to <2 years; Cohort 4 - \geq 2 years to <6 years of age). These three cohorts are of primary interest in obtaining licensure in the 15 month to 5 year age range and addressing the Center for Drug Evaluation (CDE) request to obtain data in this age group. Immune responses before and after the last vaccination in each of these age groups will be measured and used as a surrogate of efficacy. Post vaccination serotype specific serum anticapsular immunoglobulin G (IgG) responses in Cohorts 2, 3, and 4 will be compared to the post infant series responses in Cohort 1 as a bridge to efficacy. Cohorts 2, 3, and 4 will also include a control group vaccinated with *Haemophilus influenzae* type b (Hib) vaccine. The Hib vaccinated infants and children will serve as controls for assessment of the safety and immunogenicity of Cohorts 2, 3, and 4. In addition to serving as a bridge to efficacy for Cohorts 2, 3, and 4, Cohort 1 will provide the antibody persistence data at 12, 24, 36 and 48 months after the last vaccination required by the CDE.

An additional 280 subjects will be recruited because during the conduct of the study, 280 subjects were enrolled from town level immunization clinics which were under the Huaiyin county Center for Disease Control (CDC). Based on the China Vaccine Good Clinical Practice (GCP) guidelines it is unclear if town level immunization clinics are allowed to be included as clinical trial sites under the China regulations. In the review of procedures and data from subjects in the study there were no issues identified with regards to subject safety, data quality, or integrity.

Pri	mary Objective (Immunogenicity):	Pri	imary Endpoints (Immunogenicity):
•	To assess the immune responses to the 13 pneumococcal serotypes induced by 13vPnC in infants and children 7 months to <6 years of age (Cohorts 2, 3, and 4) compared to immune responses in infants 6 weeks to 2 months of age (Cohort 1).	•	The serotype-specific IgG geometric mean concentrations (GMCs) for each of the pneumococcal serotypes measured 1 month after the last dose of 13vPnC in Cohort 2, 3, 4 compared to IgG GMCs measured 1 month after the infant series in Cohort 1.

Primary Objective (Safety):	Primary Endpoints (Safety):
 To evaluate the safety profile of 13vPnC in infants and children 7 months to <6 years of age (Cohorts 2, 3, and 4) as measured by the incidence rates of local reactions, systemic events (including the use of antipyretic medication, and adverse events (AEs). 	 The incidence of local reactions and systemic events (including the use of antipyretic medication) in the 7 days after each vaccination (13vPnC or Hib) in Cohorts 2, 3 and 4. The incidence of AEs from the signing of the informed consent document (ICD) to 1 month after the last vaccination (13vPnC or Hib) in Cohort 2, 3 and 4. The incidence of newly diagnosed chronic medical conditions from 1 month after the last study vaccination (13vPnC or Hib) to 6 months after the last study vaccination in Cohort 2, 3 and 4. The incidence of serious adverse events (SAEs) from the signing of the informed consent document (ICD) to 6 months after the last study vaccination (13vPnC or Hib) in Cohort 2, 3 and 4.

STUDY DESIGN

Description

- This is a phase 3 randomized, open-label study to evaluate the safety, tolerability, and immunogenicity of 13vPnC of infants and young children who are naïve to pneumococcal vaccination.
- This study is open-label and subjects will receive the investigational products, 13vPnC or Hib vaccine (comparator).

		Age at first vaccination	Age at second vaccination	Age at third vaccination	Age at fourth vaccination
Cohort 1	13vPnC	42 to 56 Days of	42 to 70 Days After	42 to 70 Days	365 to 455
		Age	Visit 1	After Visit 2	Days of Age
Cohort 2	13vPnC or Hib	7 to <12 Months of Age	At Least 28 Days After Visit 1	365 Days to <450 Days of Age and at Least 56 Days After Visit 2 ^a	
Cohort 3	13vPnC or Hib	≥1 to <2 Years of Age	At Least 56 Days After Visit 1 ^b		
Cohort 4	13vPnC or Hib	≥2 to <6 Years of Age		-	

Age at Vaccination

a. Subjects in Cohort 2 randomized to Hib vaccine will not receive a vaccination at Visit 3. These subjects may receive a third dose of Hib vaccine according to local practice or national recommendations, at the discretion of the investigator.

b. Subjects in Cohort 3 randomized to Hib vaccine will not receive a vaccination at Visit 2.

STATISTICAL ANALYSIS

All of the analyses will be summarized for each cohort separately.

Immunogenicity Analysis Populations

An evaluable immunogenicity population and an all-available immunogenicity population will be defined for the immunogenicity analyses separately. The evaluable immunogenicity population will be the primary population for the immunogenicity analyses.

Safety Analysis

The safety population will be defined for safety analysis. The safety population will include all subjects who receive at least 1 dose of an investigational product.

Analysis Timing:

The primary analysis will be performed when the following data are available:

- IgG immunogenicity data 1 month after the infant series in Cohort 1;
- IgG immunogenicity data 1 month after the last dose of 13vPnC in Cohorts 2, 3, 4;
- Safety data up to 6 months after the last study vaccination for Cohorts 2, 3 and 4.

SCHEDULE OF ACTIVITIES

The schedule of activities table provides an overview of the protocol visits and procedures. Refer to the Study Procedures and Assessments sections of the protocol for detailed information on each procedure and assessment required for compliance with the protocol. The investigator may schedule visits (unplanned visits) in addition to those listed on the schedule of activities table, in order to conduct evaluations or assessments required to protect the well-being of the subject.

Visit Number	1	2	3	4	5	6	7	8 to 11
Visit Description	Vaccination	Vaccination	Vaccination	Post-	Vaccination	Post-Toddler	6-Month	Persistence
	1	2	3	Infant	4	Dose Visit	Follow-up	Blood Draws ^a
				Dose			Telephone	
x 74 4, xx 74 x	10 1 51	10 / 50	42 / 50	Visit	265 1 155	00 / 10 D	Contact	
Visit Window	42 to 56	42 to 70	42 to 70	28 to 42	365 to 455	28 to 42 Days	168 to 196 Days	Annually After
	Days of Age	Days After Visit 1	Days Alter Visit 2	Days	Days	After visit 5	Alter Last Study	VISIT 5
		v Isit I	v 1810 2	Visit 3	of Age		vaccination	
Informed consent	Х							
Review inclusion/exclusion criteria	Х							
Demography, medical history, and	Х							
physical examination								
Record nonstudy vaccines	Х	Х	Х	Х	Х	Х	Х	
Axillary temperature	Х	Х	Х		Х			
Assign subject number in the interactive	Х							
response technology (IRT) or equivalent								
system								
Obtain blood sample	Х			Х	Х	Х		Х
Vaccination and 30-minute observation	13vPnC	13vPnC	13vPnC		13vPnC			
Confirm continued eligibility		Х	Х	Х	Х	Х	Х	Х
Adverse event collection as appropriate	Х	Х	Х	Х	Х	Х	Х	Х
for visit								

Table 1.	Study Flowchart for	Cohort 1 (2 Months	[42 to 56 Days of Age a	t Consent])
----------	---------------------	---------------------------	-------------------------	-------------

a. Persistence blood draw visits will take place when the subject is 2 years, 3 years, 4 years and 5 years of age. The permitted visit windows are Visit 8: 2 Years of age to 2 years and 28 days of age; Visit 9: 3 years of age to 3 years and 28 days of age; Visit 10: 4 years of age to 4 years and 28 days of age; Visit 11: 5 years of age to 5 years and 28 days of age.

Table 2. Study I low chart for Condit 2 (7 months [210 Days] to minimum of fige at Consent
--

Visit Number	1	2	3	4	5
Visit Description	Vaccination	Vaccination	Vaccination	Post-Toddler	6-Month
	1	2	3	Dose visit	Follow-up Telephone Contect
Visit Window	210 to <365 Days of Age	At Least 28 Days After Visit 1	365 Days to <450 Days of Age and at Least 56 Days After Visit 2 ^a	28 to 42 Days After Visit 3	168 to 196 Days After Last Study Vaccination
Informed consent	Х				
Review inclusion/exclusion criteria	Х				
Demography, medical history, and physical examination	Х				
Record nonstudy vaccines	X	Х	Х	Х	Х
Axillary temperature	X	Х	X ^b		
Randomization in the interactive response technology (IRT) or equivalent system	X				
Obtain blood sample	X			Х	
Vaccination and 30-minute observation; investigational product as randomized ^e	13vPnC or Hib vaccine	13vPnC or Hib vaccine	13vPnC ^d		
Confirm continued eligibility		Х	Х	Х	
Provide parent with diary, thermometer, and measuring device, if necessary	Х	Х	X ^b		
Assess reactogenicity and the use of antipyretic medication	Days 1 to 7	Days 1 to 7	Days 1 to 7 ^b		
Review diary data			Х		
Collect the diary			X ^e	X ^b	
Adverse event collection as appropriate for visit	X	Х	Х	Х	Х

a. The third dose must be given at age 12 months to less than 15 months of age and at least 56 days after the second vaccination.

b. 13vPnC recipients only.

c. Subjects will receive 13vPnC or active comparator (*Haemophilus influenzae* type b vaccine [Hib vaccine]) according to age-appropriate schedules.

d. Subjects randomized to Hib vaccine will not receive a vaccination at Visit 3. Subjects randomized to Hib may receive a third dose of Hib vaccine according to local practice or national recommendations, at the discretion of the investigator.

e. Hib vaccine recipients only.

Table 5. Sludy Flowchart for Conort 5 (≥ 1 fear to ~ 2 fears of Age at Consen	Table 3.	Study Flowchart for Ce	Cohort 3 (≥1 Year to <2 Years of Age at (Consent)
--	----------	------------------------	---	----------

Visit Number	1	2	3	4
Visit Description	Vaccination 1	Vaccination 2	1 Month After Visit 2	6-Month Follow-up Telephone Contact
Visit Window	≥1 to <2 Years of Age	At Least 56 Days After Visit 1	28 to 42 Days After Visit 2	168 to 196 Days After Last Study Vaccination
Informed consent	Х			
Review inclusion/exclusion criteria	Х			
Demography, medical history, and physical examination	Х			
Record nonstudy vaccines	Х	Х	Х	Х
Axillary temperature	Х	X ^a		
Randomization in the interactive response	Х			
technology (IRT) or equivalent system				
Obtain blood sample	Х		Х	
Vaccination and 30-minute observation;	13vPnC or	13vPnC ^c		
investigational product as randomized ^b	Hib vaccine			
Confirm continued eligibility		X	Х	
Provide parent with diary, thermometer, and	Х	X^{a}		
measuring device, if necessary				
Assess reactogenicity and the use of antipyretic	Days 1 to 7	Days 1 to 7^{a}		
medication				
Review diary data		XX		
Collect the diary		X ^d	X ^a	
Adverse event collection as appropriate for	Х	Х	Х	Х
visit				

a. 13vPnC recipients only.
b. Subjects will receive 13vPnC or active comparator (*Haemophilus influenzae* type b vaccine [Hib vaccine]) according to age-appropriate schedules.
c. Subjects randomized to Hib vaccine will not receive a vaccination at Visit 2.

d. Hib vaccine recipients only.

Visit Number	1	2	3
Visit Description	Vaccination	1 Month	6-Month
	1	After Vaccination 1	Follow-up Telephone Contact
Visit Window	≥2 to <6 Years of Age	28 to 42 Days After Visit 1	168 to 196 Days
			After Visit 1
Informed consent	Х		
Review inclusion/exclusion criteria	Х		
Demography, medical history, and	Х		
physical examination			
Record nonstudy vaccines	Х	Х	Х
Axillary temperature	Х		
Randomization in the interactive	Х		
response technology (IRT) or			
equivalent system			
Obtain blood sample	Х	Х	
Vaccination and 30-minute	13vPnC or		
observation; investigational product as	Hib vaccine		
randomized ^a			
Confirm continued eligibility		Х	
Provide parent with diary,	Х		
thermometer, and measuring device, if			
necessary			
Assess reactogenicity and the use of	Days 1 to 7		
antipyretic medication			
Review diary data		X	
Collect the diary		Х	
Adverse event collection as	X	X	X
appropriate for visit			

Table 4. Study Flowchart for Cohort 4 (≥2 Years to <6 Years of Age At Consent)

a. Subjects will receive 13vPnC or active comparator (Haemophilus influenzae type b vaccine [Hib vaccine]) according to age-appropriate schedules.

1. INTRODUCTION

1.1. Indication

Prevenar 13® is licensed in China for active immunization for the prevention of invasive pneumococcal disease caused by *Streptococcus pneumoniae* serotypes 1, 3, 4, 5, 6A, 6B, 7F, 9V, 14, 18C, 19A, 19F, and 23F (including bacteremic pneumonia, meningitis, septicemia, and bacteremia) in infants and children from 6 weeks to 15 months of age. *S pneumoniae* is the most common cause of invasive disease as well as pneumonia and upper respiratory tract infections.

This study is to seek an additional indication for licensure for active immunization for the prevention of invasive pneumococcal disease caused by *S pneumoniae* serotypes 1, 3, 4, 5, 6A, 6B, 7F, 9V, 14, 18C, 19A, 19F, and 23F (including sepsis, meningitis, bacteremia) in children from 15 months to 5 years of age.

1.2. Background and Rationale

S pneumoniae causes invasive pneumococcal disease (IPD), including bacteremia, sepsis, and meningitis) in infants and young children throughout the world. Noninvasive pneumococcal diseases, including otitis media, sinusitis, and bronchitis, are less severe but much more common than invasive disease, so also pose a significant disease burden. *S pneumoniae* also causes bacteremic and nonbacteremic pneumonia.

According to the World Health Organization (WHO), there is a high burden of pneumococcal disease and it is estimated that 1.6 million people die each year from the disease, 0.7 to 1 million of whom are children aged less than 5 years.¹ Pneumonia was the leading cause of death from 1996 to 2000 in children under 5 years of age² and data reported by WHO/United Nations Children's Fund (UNICEF) indicate that 72,000 children less than 5 years of age died of all-cause pneumonia in China in 2004.³ Pneumococcal meningitis is a severe disease with high mortality and high incidence of neurological sequelae.

In an epidemiological study conducted in 18 provinces and cities in China from 1982 to 1985, 482 out of 10,446 cases of bacterial pneumonia, meningitis, and otitis media were caused by culture-confirmed *S pneumoniae*.⁴ The percentages of bacterial pneumonia, meningitis, and otitis media caused by *S pneumoniae* were 1.4%, 7.9%, and 6.8%, respectively. Between 40% and 73% of the infections caused by *S pneumoniae* were in infants and children less than 3 years old. The overall mortality of pneumonia and meningitis caused by culture-confirmed *S pneumoniae* was 16% for both conditions, but in infants less than 1 year old it was as high as 29% and 17%, respectively. Major pathogens causing lower respiratory tract infections in young children are *S pneumoniae* and *H influenzae* and the proportion of lower respiratory tract infections caused by *S pneumoniae* is 13% to 53% depending on the age group.^{5,6,7} In a systematic review of *S pneumoniae* and the average percentages of cases of meningitis due to *S pneumoniae* were 5% (95% confidence interval [CI]: 2-12%) among 0 – 4 years old and 28% (95% CI: 17-45%) in older children and adults.⁸

A 23-valent pneumococcal polysaccharide vaccine (PPSV23) has been available for many years, but as with other polysaccharide (PS) vaccines, it is not effective in infants.

According to published reports, very high prevalence rates of beta-lactam and macrolide resistance in *S pneumoniae* have been found in Asian countries. Particularly erythromycin, where >70% of clinical isolates were fully resistant. Prevalence rate of penicillin resistance was 57.5% for meningeal isolates. Fully penicillin resistant isolates were 2.2% and erythromycin resistant isolates were 96.4%.⁹ In a study in China involving 11 sites looking at IPD isolates among children <14 years old revealed the most common serotypes isolated were 19F, 14, 19A, 6B and 23F. These serotypes accounted for 73.1% of all isolates.¹⁰ Due to the high level of antibiotic resistance and high incidence of IPD, vaccines are important in the attempt to control pneumococcal disease.¹¹

In 2005, clinical trials with Prevenar were conducted in China. In the phase 3 study involving Chinese infants, Prevenar was shown to be immunogenic, well-tolerated and safe when given either separately or concomitantly with a diphtheria, tetanus, and acellular pertussis (DTaP) vaccine at 3, 4, and 5 months of age. In a subset of these infants completing a 3-dose primary vaccination series with Prevenar, more than 92% of subjects achieved antibody concentrations $\geq 0.35 \ \mu g/mL$ for each of the vaccine serotypes, except for serotype 6B, which was 83%.¹²

13vPnC is licensed in the European Union and other European countries, the United States, and other countries globally, now including China, as Prevenar 13/Prevnar 13®. It contains polysaccharides from the 7 serotypes included in 7-valent pneumococcal conjugate vaccine (7vPnC) and an additional 6 serotypes (1, 3, 5, 6A, 7F, and 19A), all conjugated to cross-reactive material 197 (CRM₁₉₇). It has been shown that the 6 additional serotypes in 13vPnC increase coverage for IPD prevention in children <5 years of age to 74% to 88% globally.¹³ Importantly, the additional serotypes in 13vPnC are associated with a high percentage of pneumococcal disease in the developing world.^{14,15} Local serotype coverage in China of 13vPnC can range from 80.5% to as high as 87.2%. There is also some regional difference where Northern China appears to have serotype coverage of 75% as compared to Southern China that has serotype coverage of 92%.^{16,17,18,19,20}

Prevenar 13, the 13-valent pneumococcal conjugate vaccine (13vPnC) was approved in China in October 2016 for the prevention of invasive pneumococcal disease in infants 6 weeks to 15 months of age. The approved regimen only allows vaccination with Prevenar 13 at 2, 4, 6 months for the primary series and the toddler or booster dose at 12 to 15 months of age. Prevenar, the 7-valent vaccine that was used as a comparator in the Phase 3 study in China had been approved through 5 years of age (up to the 6th birthday). The safety and immunogenicity of 7vPnC in children 7 months up to 5 years of age had been assessed in a post-licensure study (Study number B1841008).

The Center for Drug Evaluation (CDE) requested that safety and immunogenicity of Prevenar 13 be assessed in children 7 months to 5 years of age (before the 6th birthday). CDE also requested that Pfizer provide antibody persistence data through 5 years of age in children vaccinated as infants. This study is designed to support licensure of 13vPnC from

7 months through 5 years of age and to address both of these post licensure commitments from the CDE.

This study includes 4 separate cohorts broken down by age. Cohorts 2, 3 and 4 range in age from 7 months to 5 years of age (Cohort 2 - 7 months to <12 months of age; Cohort 3 - ≥ 1 year to <2 years; Cohort 4 - ≥ 2 years to <6 years of age). These three cohorts are of primary interest in obtaining licensure in the 7 months to 5 year age range and addressing the CDE request to obtain safety and immunogenicity data in this age group. Immune responses before and after the last vaccination in each of these age groups will be measured and used as a surrogate of efficacy. Cohort 1 will include infants 6 weeks to 2 months of age that will be vaccinated with 13vPnC according to the currently licensed infant schedule (2, 4, 6 and 12 to 15 months). Post vaccination serotype specific serum anticapsular IgG responses in Cohorts 2, 3, and 4 will be compared to the post infant series responses in Cohort 1 as a bridge to efficacy. Cohorts 2, 3, and 4 will also include a control group vaccinated with *Haemophilus influenzae* type b (Hib) vaccine. The Hib vaccinated infants and children will serve as controls for assessment of the safety and immunogenicity of Cohorts 2, 3, and 4.

In addition to serving as a bridge to efficacy for Cohorts 2, 3, and 4, Cohort 1 will provide the antibody persistence data at 12, 24, 36 and 48 months after the last vaccination required by the CDE.

During the conduct of the study at the Huaiyin county CDC, 280 subjects were enrolled from town level immunization clinics which were under the Huaiyin county CDC. According to the China Vaccine GCP guidelines²¹ it is unclear if town level immunization clinics are allowed under the China regulations to be included as clinical trial sites. In reviewing the procedures and data from subjects in the study there were no issues identified with regards to subject safety, data quality, or integrity. An additional 280 subjects will be recruited. The purpose of enrolling these additional 280 subjects is to mitigate the possible risk that the previous 280 enrolled subjects from the town level immunization clinics will not be able to support approval/licensure of 13vPnC for infants and children 7 months through 5 years of age. All additional subjects (total 280) will follow the same study procedures and analyses.

Additional information for this compound may be found in the single reference safety document (SRSD), which for this study is the Investigator Brochure. The SRSD for the Hib vaccine is the local package insert.

Primary Objective (Immunogenicity):Primary Endpoints (Immunogenicity):• To assess the immune responses to the 13
pneumococcal serotypes induced by 13vPnC in
infants and children 7 months to <6 years of age
(Cohorts 2, 3, and 4) compared to immune
responses in infants 6 weeks to 2 months of age
(Cohort 1).• The serotype-specific IgG geometric mean
concentrations (GMCs) for each of the
pneumococcal serotypes measured 1 month after
the last dose of 13vPnC in Cohort 2, 3, 4
compared to IgG GMCs measured 1 month after
the infant series in Cohort 1.

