2. STUDY OBJECTIVES AND ENDPOINTS

Primary Objective (Safety):	Primary Endpoints (Safety):
 To evaluate the safety profile of 13vPnC in infants and children 7 months to <6 years of age (Cohorts 2, 3, and 4) as measured by the incidence rates of local reactions, systemic events (including the use of antipyretic medication, and adverse events (AEs). 	 The incidence of local reactions and systemic events (including the use of antipyretic medication) in the 7 days after each vaccination (13vPnC or Hib) in Cohorts 2, 3 and 4. The incidence of AEs from the signing of the informed consent document (ICD) to 1 month after the last vaccination (13vPnC or Hib) in Cohort 2, 3 and 4. The incidence of newly diagnosed chronic medical conditions from 1 month after the last study vaccination (13vPnC or Hib) to 6 months after the last study vaccination in Cohort 2, 3 and 4. The incidence of serious adverse events (SAEs) from the signing of the informed consent document (ICD) to 6 months after the last study vaccination (13vPnC or Hib) in Cohort 2, 3 and 4.
Secondary Objectives (Immunogenicity):	Secondary Endpoints (Immunogenicity):
• To describe the functional antibody responses as measured by opsonophagocytic activity (OPA) to the 13 pneumococcal serotypes induced by 13vPnC in infants and children 7 months to <6 years of age (Cohorts 2, 3, and 4) compared to responses in infants 6 weeks to 2 months of age (Cohort 1).	• The serotype-specific OPA geometric mean titers (GMTs) for each of the pneumococcal serotypes measured in a subset of approximately 50 subjects per cohort measured 1 month after the last dose of 13vPnC in Cohort 2, 3, 4 compared to OPA GMTs measured 1 month after the infant series in Cohort 1.
• To describe the immune responses to 13vPnC compared to Hib vaccinated controls in Cohorts 2, 3, and 4.	 Serotype specific IgG GMC in all subjects and OPA GMTs in approximately 50 subjects per cohort vaccinated with 13vPnC (Cohorts 1,2,3 4) and approximately 25 subjects per cohorts vaccinated with Hib (Cohort 2, 3, 4) using blood drawn at the following visits: Cohort 2: Visit 1, Visit 4 Cohort 3: Visit 1, Visit 3 Cohort 4: Visit 1, Visit 2
• To describe the circulating antibody levels to the 13 pneumococcal serotypes from before vaccination through 5 years of age (4 years after the last study vaccination) in Cohort 1.	• Serotype specific IgG GMC in all subjects and OPA GMTs in approximately 50 subjects at all times points in Cohort 1.

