3.2. Approximate Duration of Subject Participation

Subjects in Cohort 1 are expected to participate from the first vaccination to the final visit which will include an antibody persistence blood draw 4 years after the last 13vPnC vaccination.

Subjects in Cohorts 2, 3 and 4 are expected to participate from the first vaccination to the final phone call, which will be the 6 months after the last vaccination.

The total duration of subject participation is up to approximately:

- Subjects in Cohort 1 will participate for up to approximately 5 years
- Subjects in Cohort 2 will participate for up to approximately 14 months
- Subjects in Cohort 3 will participate for approximately 8 months
- Subjects in Cohort 4 will participate for approximately 6 months

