3.3. Approximate Duration of the Study

This study is anticipated to last approximately 66 months, assuming a 6-month recruitment period. The total duration may differ depending on the actual enrollment rate. Enrollment into the 4 cohorts will take place simultaneously. The end of the study is the last visit of the last subject in Cohort 1, which is scheduled approximately 48 months after the last vaccination.

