6.1.5. Cohort 1: Visit 5, Vaccination 4 (365 to 455 Days of Age)

- Based on clinical evaluation, determine whether any SAEs and newly diagnosed chronic medical conditions have occurred since the last study visit and record them on the CRF.
- Record any nonstudy vaccinations.
- On the day of vaccination, measure and record the subject's axillary temperature.
- Ensure that the subject continues to be eligible for the study; refer to Subject Withdrawal section of the protocol.
- Ensure the subject does not meet any of the temporary delay criteria.
- Collect a blood sample (approximately 5 mL). Blood must be drawn from peripheral veins (eg, arm, foot, or scalp veins). Drawing blood from central veins (eg, jugular or femoral veins), which may increase the risk associated with study participation, is not permitted.
- Administer a single 0.5-mL intramuscular injection of 13vPnC into the subject's left limb (left anterolateral thigh muscle or deltoid of the left arm) in accordance with the local package insert.
- Observe the subject for at least 30 minutes after vaccination for any significant acute reactions. Any AE noted during the observation period should be recorded in the source documents and in the AE section of the CRF.
- Ask the caregiver to contact the investigator or other site staff immediately if any significant illness or hospitalization occurs during the study period.
- Schedule an appointment with the caregiver for the next study visit.
- The investigator or an authorized designee completes the CRF and updates the investigational product accountability records.

6.1.6. Cohort 1: Visit 6, Post-Toddler Dose Follow-up (28 to 42 Days After Visit 5)

- Based on clinical evaluation, determine whether any AEs (including SAEs) have occurred since the last study visit and record them on the CRF.
- Record any nonstudy vaccinations.
- Ensure that the subject continues to be eligible for the study; refer to Subject Withdrawal section of the protocol.
- Collect a blood sample (approximately 5 mL). Blood must be drawn from peripheral veins (eg, arm, foot, or scalp veins). Drawing blood from central veins (eg, jugular or femoral veins), which may increase the risk associated with study participation, is not permitted.
- Schedule an appointment with the caregiver for the 6-month follow-up telephone contact.
- The investigator or an authorized designee completes the CRF and updates the investigational product accountability records.

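### Do the Cohort 1 persistence draws miss the stated 12, 24, 36 and 48 months after the last vaccination?

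*Protocol*

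**What the plan says.** Two anchors appear for the Cohort 1 persistence samples.

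**Time since dose 4.** The Protocol Summary and section 1.2 both state that "Cohort 1 will provide the antibody persistence data at 12, 24, 36 and 48 months after the last vaccination required by the CDE". The window row of protocol Table 1 has "Annually After" Visit 5 for Visits 8 to 11. Section 3.2 mentions an "antibody persistence blood draw 4 years after the last 13vPnC vaccination", and section 3.3 describes the last Cohort 1 visit as one "which is scheduled approximately 48 months after the last vaccination". Sections 7.5.1 and 7.5.2 describe yearly sampling over four years following the last dose.

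**Age.** Table 1 footnote a, which is attached to the same column, gives "Visit 8: 2 Years of age to 2 years and 28 days of age" and matching windows for Visits 9 to 11 at ages 3, 4 and 5. Sections 6.1.8 to 6.1.11 repeat these windows as visit headings. Section 1.2 also reports the regulator's request by age: "CDE also requested that Pfizer provide antibody persistence data through 5 years of age in children vaccinated as infants".

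The secondary objective (protocol section 2, repeated in SAP 2.1.3) uses both anchors: antibody levels are described "through 5 years of age (4 years after the last study vaccination) in Cohort 1".

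The last vaccination has its own window. Section 6.1.5 allows dose 4 from 365 to 455 days of age.

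**The concern.** If draws follow birthdays and dose 4 can be given anywhere in a 90-day span, time since dose 4 is not fixed at whole years. The departure is lopsided: a compliant draw can be about three months early but less than one month late. Where antibody wanes, early sampling tends to flatter persistence, most of all at the first time point, where three months is a quarter of the stated interval.

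The SAP does not settle the matter. Section 6.2.1 refers to all Cohort 1 time points and plots them without naming a time scale. The required post-dose draw windows in SAP 4.1 cover only the one-month samples. No planned table shows actual days from dose 4 to Visits 8 to 11. These data answer a regulatory commitment, so a report that took its labels from section 1.2 would state intervals that the schedule does not guarantee.

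**Working it through.** **Inputs.** Dose 4 at 365 to 455 days of age (protocol 6.1.5). Draw from birthday *y* to birthday *y* + 28 days, with *y* = 2, 3, 4, 5 for Visits 8 to 11 (Table 1 footnote a; 6.1.8 to 6.1.11). Conventions: year = 365.25 days, month = 365.25/12 = 30.4375 days.

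**Reproducing the stated figure.** With dose 4 on day 365 and the draw on the birthday, the interval is 365.25*y* - 365. Visit 8 gives 730.5 - 365 = 365.5 days, or 12.01 months. Visit 11 gives 1826.25 - 365 = 1461.25 days, or 48.01 months. The stated 12, 24, 36 and 48 months thus describe a child vaccinated at the start of the window and sampled on the birthday.

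**Permitted range.** Shortest = 365.25*y* - 455. Longest = 365.25*y* + 28 - 365.

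| Visit | Shortest (days) | Longest (days) | Months | Stated |
|---|---|---|---|---|
| 8 | 730.5 - 455 = 275.5 | 730.5 - 337 = 393.5 | 9.1-12.9 | 12 |
| 9 | 1095.75 - 455 = 640.75 | 1095.75 - 337 = 758.75 | 21.1-24.9 | 24 |
| 10 | 1461 - 455 = 1006 | 1461 - 337 = 1124 | 33.1-36.9 | 36 |
| 11 | 1826.25 - 455 = 1371.25 | 1826.25 - 337 = 1489.25 | 45.1-48.9 | 48 |

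With 365-day years or true calendar birthdays the limits move by at most about 0.05 month.

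**Departure from the stated time.** It is the same at every visit: 365.25 - 275.5 = 89.75 days early (2.9 months) to 393.5 - 365.25 = 28.25 days late (0.9 month). As a share of the stated interval, the largest shortfall is 89.75/365.25 = 24.6% at Visit 8 and 89.75/1461 = 6.1% at Visit 11. For a dose at mid-window (day 410), Visit 8 falls at 320.5 to 348.5 days, or 10.5 to 11.4 months.

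**How often the stated time can be met.** Demanding the exact day, it can be met for dose ages 366 to 393, 28 of the 91 permitted days (29 if a year is taken as 365 days). Allowing one month either side (my assumption), it can be met for dose ages 365 to 423, 59 of 91. These are counts of calendar days, not of children; the documents give no distribution of age at dose 4.

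**Spacing between draws.** Consecutive draws in one child are 365.25 ± 28 days apart, that is 337.25 to 393.25 days. A child's age at dose 4 shifts all four draws by the same amount, so the yearly spacing along the curve holds.

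**Where the times are used.** The Cohort 1 endpoint is GMCs and GMTs at all time points. The summaries and plots in SAP 5.2.2 and 6.2.1 are by time point and carry no month labels. SAP 5.2.2 also compares the persistence samples with prevaccination samples from Cohorts 2 to 4, which are defined by age. SAP 6.3.1.1 already tabulates draws inside, before and after the protocol time frame. No hypothesis, margin or stopping rule depends on months since dose 4.

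**The case for a change.** The best case for acting is this. The sentence in the Protocol Summary and section 1.2 carries no qualifier such as approximately, and it ties the times to what the regulator required. A draw at 9.1 months would count as on time in the SAP's timing table, and no planned output would show it. Labelling by scheduled age and adding a four-row table of days since dose 4 would need no new data and would serve either reading of the request.

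Part of this stands. That sentence is tighter than the schedule supports, and a report should not present the visits as exact months since dose 4.

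The rest carries less weight:

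- The conflict is narrower than the number of places suggests. Section 3.3 says approximately, and section 3.2 sits under a heading about approximate duration. Sections 7.5.1 and 7.5.2 can be read as spacing between draws, which is close to yearly. The Table 1 cell is governed by its own footnote, and the objective leads with age.
- The harm depends on labels that no SAP output specifies. Visits 8 to 11 are already defined by number and age, and the axis scale of a plot is settled in the output shells.
- A table of days since dose 4 would be a useful extra, not the repair of an error. Without a waning rate or an age distribution at dose 4, no size can be put on any flattering of persistence.

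**Conclusion.** The inconsistency is genuine but clerical. One background sentence, printed twice, gives whole-year intervals since dose 4, while the schedule fixes the draws by age; the permitted intervals run from 89.75 days short of the stated times to 28.25 days beyond them. No change to the plan follows. Sites work from unambiguous windows, the SAP prints no month labels for these samples, and the objective is secondary and descriptive. The primary comparison, type I error and power do not involve Visits 8 to 11. Analysts can be expected to report the visits by number or scheduled age, and can derive time since dose 4 from recorded dates if the regulator asks for it.

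This rests on the windows as printed, on a year of 365.25 days (other conventions give the same conclusion), and on the absence of any decision rule using these times. How the regulator worded its request is not shown in the documents. If the two descriptions in section 1.2 are reconciled in a later amendment, that is an editorial matter; this review takes no position on dose or visit timing.
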